1.3.3. Safety Endpoints

Safety endpoints which will include:

- Adverse events
- Vital signs and weight
- Physical Exams

- Laboratory tests (serum chemistry, hematology, coagulation, urinalysis)
- Echocardiogram
- Electrocardiograms (ECGs)
- Use of concomitant medications

2. PROCEDURES

2.1. General Overview of Procedures

Ionis Pharmaceuticals, Inc. (or designee) will review all study data including source documents, CRFs, and laboratory reports. The study site will enter patient source data into the case report form. Some laboratory data will be transferred electronically from Endocrine Lab, Ludwig-Maximilians-University (LMU) Munich via Medpace Reference Laboratories (MRL), and from Pharmaceutical Product Development (PPD) Inc. (plasma concentration data) to Ionis Pharmaceuticals, Inc.

2.2. Randomization & Treatment Allocation

Patients will be randomized after all screening assessments have been completed and after the Investigator has verified that they are eligible per criteria in protocol Sections 5.1 and 5.2. No subject may begin treatment prior to randomization and assignment of a unique subject identification number.

Eligible patients will be randomized to receive a planned monthly ISIS 766720 SC injection as outlined in protocol Section 3.4.2.

The Sponsor or designee will prepare the randomization list and utilize an automated IRT (Interactive Response Technology) system for randomization assignment.

2.3. Conduct

The study will be conducted in accordance with current Good Clinical Practice (GCP) and International Conference on Harmonization (ICH) guidelines, the World Medical Association Declaration of Helsinki guidelines, the Food and Drug Administration (FDA) Code of Federal Regulations, and all other local regulatory requirements.

2.4. Data Monitoring

2.4.1. Safety Data Monitoring

Ionis Pharmaceuticals, Inc. (or designee) is responsible for processing all reported adverse events (AEs). All serious adverse events (SAEs), reported to Ionis Pharmaceuticals, Inc. (or designee), will be reviewed according to standard operating procedures. The medical monitor will review all AEs and SAEs on an ongoing basis throughout the study. Ionis Pharmaceuticals, Inc. (or designee) will prepare and submit safety reports to the health authorities worldwide in accordance with local requirements. If it becomes necessary to communicate new safety information, Ionis Pharmaceuticals, Inc. (or designee) will also prepare a safety notification letter and transmit it to all applicable study sites.

2.5. Data Management

An electronic case report form (eCRF) utilizing an Electronic Data Capture (EDC) application will be used for this Study.

2.5.1. Case Report Form Data

BioClinica, Inc. is responsible for creating the EDC data entry screens, database and edit checks using definitions developed by Ionis Pharmaceuticals, Inc. Ionis Pharmaceuticals, Inc. is responsible for the review, data management querying and locking of the database.

Data are single-entered into the EDC system by the investigator site staff. Programmed edit checks (computer logic that checks the validity of the data entered and also prompts for missing data that is expected to be entered) are run and automatic queries are generated. Ionis Pharmaceuticals, Inc. reviews all data for accuracy and validity and generates additional queries in the EDC system when necessary. The data is corrected or an explanation concerning the query is provided in the EDC system. After all data is entered, source data verified, reviewed

and queried the database is closed. The data is then reviewed by Ionis Pharmaceuticals, Inc. and additional queries may be generated. After all queries are resolved the database is locked.

2.5.2. Laboratory Data

Ionis Pharmaceuticals, Inc. is responsible for the format of the laboratory electronic data transfers, the transfer schedule, and the review of the clinical laboratory data. Investigator sites have access to the data via lab reports sent directly from the laboratory and online using the MRL ClinTrack® database. The laboratory data will be stored as SAS datasets.

2.5.3. Pharmacokinetics (PK) Data

Ionis Pharmaceuticals, Inc. is responsible for the management and review of the plasma ISIS 766720 concentration data from PPD. This review process involves reconciling the patient and visit identifiers (i.e., patient demographics) with the clinical data collected in the EDC system. The final PK data will be stored as CSV and/or EXCEL files. Final data, which has been approved by Quality Assurance, will be stored in the Sponsor's document management system.

3. ANALYTICAL PLAN

3.1. Statistical Design Summary

This is a Phase 2, randomized, open label multi-center study. Approximated 40 eligible patients will be randomized into one of the three treatment groups [REDACTED]

The primary endpoint is the percent change from Baseline to Week 27 in serum IGF-1 and analyzed by one-sample t-test with an alpha level of 5%. The statistical outcomes are summarized by the ISIS 766720 dose received [REDACTED] and overall.

Additional summary by the adjusted dose (refer to protocol Section 8.7) received may be provided.

An interim analysis may be conducted when approximately 50% of patients complete the primary efficacy assessment. The primary analysis will take place after all patients complete Treatment Period and the database has been locked.

3.2. General Overview of Analyses

3.2.1. Statistical Methods

Descriptive summary statistics including number of patients, mean, median, standard deviation, standard error of mean, 25th percentile, 75th percentile, minimum, and maximum for continuous variables, and counts and percentages for categorical variables will be provided to summarize most data. The study outcomes will be summarized by treatment groups. The efficacy endpoints

will be assessed on the FAS and PPS with the latter being the basis for the primary efficacy analysis. The safety analyses will be performed on the Safety Set. Pharmacokinetic analysis will be conducted in the PK Set.

For the continuous outcomes, the data will be analyzed using one-sample t-test to evaluate the estimate percent changes are different than zero. For the categorical outcomes, the data will be analyzed by using one-sample binomial Exact test ([Clopper and Pearson 1934](#)) to evaluate whether the estimate proportions are deviated from zero. The normality assumption for one-sample t-test model will be assessed by the Shapiro-Wilk test. In the case of data departs substantially from normality, the nonparametric Wilcoxon signed rank test will be applied instead. All statistical tests will be conducted using 2-sided tests with 5% Type I error rate unless otherwise stated. Where appropriate, P-values will also be provided as an indicator to summarize how much deviation from zero within each treatment group based on the statistical tests.

Additional summary of between treatment group comparison may be provided. Treatment group and the stratification factor are included as the independent variables in the statistical model while comparing among treatment groups. For the continuous endpoints, the ANCOVA or ANOVA model will be applied depending on the independent variables or van Elteren test if the data departs substantially from normality. For the dichotomous endpoints, logistic regression will be used instead.

Additional subject listings included case report form (CRF) data and derived outcomes from the data may be presented.

Baseline definition:

Due to the variance of IGF-1 between Screening and Day 1, baseline of IGF-1 is defined as the average value of Screening and Day 1 prior to the first administration of ISIS 766720. Multiple results with the same visit label will be averaged first, and baseline IGF-1 will be calculated as IGF-1 at Screening plus IGF-1 at Day 1 divide by 2.

For other endpoints, baseline is defined as the last non-missing value prior to the first administration of ISIS 766720.

Analytical visits:

In general, all post-baseline data will be summarized using the visit labels provided in the data. Multiple results with the same visit label will be averaged for the continuous variables, and the worst result will be used for the categorical variables. Results with visit labels as “Unscheduled” will not be included in the by-visit summary tables and figures except for determining baseline and the incidence of abnormality lab summary including AST, ALT, platelet and renal but will be presented in data listings.

For patients who had last dose prior to treatment termination, PD results greater than 3 weeks after the last dose (the date of last dose + 21 days) up to treatment termination will not be included in the by-visit summary tables and figures. Also, for patients who started other acromegaly medications in the post-treatment period, PD results after the start date of acromegaly medication will not be included in the by-visit summary tables and figures.

Other situations, such as required additional confirmation, will be described separately in the related endpoint analysis approach.

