3.3. Number of Patients

Approximately 40 patients are planned to be randomized in the study. Thirty-six (36) patients (12 in each treatment group) in the per protocol set (PPS) are needed to complete the Treatment Period and the primary efficacy endpoint. [REDACTED]

[REDACTED]

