10.6.3. Efficacy Analysis

The primary analysis will be the comparison of percent change from Baseline to Week 27 in serum IGF-1. The null hypothesis of no percentage change in serum IGF-I levels from Baseline to Week 27 will be tested for each treatment group in the PPS. The data will be analyzed using a one-sample t-test with an alpha level of 5%. Ninety-five percent (95%) confidence interval of estimated percent reduction within treatment group will also be provided. In the case data departs substantially from normality, the nonparametric test will be employed instead. The primary analysis will take place after all patients complete Treatment Period and the database has been locked.

The primary efficacy endpoint will also be assessed, as a secondary analysis, in the FAS.

Additional secondary efficacy analyses are:

- change and percent change from Baseline to each schedule post-baseline visit in serum IGF-1 by the ISIS 766720 treatment groups in the PPS and FAS. The data will be analyzed in a similar way to the primary analysis
- proportion of patients achieve normalized IGF-1 levels to within 1.2 times of gender and aged limits within each ISIS766720 treatment groups will be assessed by an exact binomial test in the PPS and FAS.
- proportion of patients achieve normalized IGF-1 levels to within 1.0 times of gender and aged limits within each ISIS 766720 treatment groups will be assessed by an exact binomial test in the PPS and FAS

Further details will be described in the Statistical Analysis Plan (SAP).

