1. INTRODUCTION

This document provides a description of the study organization, study procedures, and the plan for the statistical analysis of the study data. Section 1 discusses study design, objectives, and endpoints; Section 2 provides the study procedures; Section 3 provides the detailed plan for the statistical analyses.

The purpose of this plan is to provide specific guidelines from which the analysis will proceed. Any deviations from these guidelines will be documented in the clinical study report (CSR).

Within this document, the terms ‘patient’ and ‘subject’ are both used to describe the individual who enrolls in this study.

[figure not shown]

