3.4.2. Analysis of Secondary Endpoints

The analysis population will be conducted in both FAS and PPS. The results will be summarized by the ISIS 766720 dose received at randomization and overall. In addition, the results will also be summarized by the maximum ISIS 766720 dose received through the study and overall.

Subset analysis will be conducted among uncontrolled population ($IGF-1 > 1.3 \times ULN$ at Day 1) and high-strata IGF-1 population ($IGF-1 > 2.5 \times ULN$ at Screening), separately.

Proportion of subject incidence of achieving within 1.2 times, achieving 1.0 times of ULN over time will be summarized at each scheduled visit respectively. The estimated proportion with 95% confidence interval will be provided.

Absolute, change and percent change from Baseline to each scheduled post-baseline visit in IGF-1 over time will be summarized at each scheduled visit.

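### The exact binomial test of the IGF-1 normalisation rates is set against a null of zero, so its p-value only records whether any patient responded

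*Combined protocol and SAP*

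**What the plan says.** SAP 3.2.1 (Statistical Methods) gives one rule for all categorical outcomes: a one-sample exact binomial test, citing Clopper and Pearson, used "to evaluate whether the estimate proportions are deviated from zero". Tests are two-sided at 5%. The section then states the purpose of the p-values, to be given where appropriate: "P-values will also be provided as an indicator to summarize how much deviation from zero within each treatment group".

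The outcomes concerned are the two secondary endpoints, IGF-1 within 1.2 and within 1.0 times the age and sex limits at Week 27. Protocol 10.6.3 says that each of these proportions, within each treatment group, "will be assessed by an exact binomial test in the PPS and FAS". It states no null value and leaves further detail to the SAP.

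SAP 3.4.1 defines a responder as a ratio of IGF-1 to ULN of at most 1.2 or 1.0. SAP 3.4.2, which is specific to these endpoints, names neither a test nor a null, but does say: "The estimated proportion with 95% confidence interval will be provided". It does not name the interval method there. No non-zero reference rate appears in the visible analysis text.

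**The concern.** A null proportion of exactly zero is a boundary value at which the binomial distribution has no spread. One responder already contradicts it with certainty, and further responders cannot add to that. The test reduces to asking whether at least one patient was normalised, which the responder count shows directly.

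The SAP, however, asks the p-value to convey the amount of deviation from zero. A table printing p < 0.0001 beside 1/12 would look like strong evidence of normalisation when it records one patient. It would print the same value beside 12/12. What is at stake is a misleading significance statement on two secondary endpoints, not the estimates themselves.

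**Working it through.** **Inputs.** Null proportion 0, exact binomial test, two-sided 5% (SAP 3.2.1). Group size 12: "Thirty-six (36) patients (12 in each treatment group) in the per protocol set (PPS) are needed" (Protocol 3.3), so 36 overall.

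**The plan's own figure.** The documents give no power, sample size or p-value for the binomial test. The one stated figure is for the primary endpoint (SAP 3.3.3): a 27.5% reduction with SD 30%, two-sided one-sample t-test at 5%. The standardised effect is 27.5/30 = 0.917. Noncentral-t power is 78.2% at n = 11 and 82.4% at n = 12, so 12 is the smallest n that reaches 80%. Allowing for 10% dropout, 36/(1 − 0.10) = 40. That figure reproduces, and the present point does not touch it.

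**The p-value under a zero null.** For X responders among n, with π = 0:

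P(X = x) = C(n, x) · 0^x · 1^(n − x), which is 1 at x = 0 and 0 at every x ≥ 1.

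The exact p-value sums the probabilities of outcomes at least as extreme as the one observed. It is therefore 1 at x = 0 and 0 at every x ≥ 1, one-sided or two-sided, for every n. Direct computation at n = 12, 24 and 36 agrees.

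**Compared with the interval.** The Clopper-Pearson 95% limits are the 0.025 quantile of Beta(x, n − x + 1) and the 0.975 quantile of Beta(x + 1, n − x), with 0 as the lower limit at x = 0 and 1 as the upper limit at x = n.

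| Responders | p against 0 | Clopper-Pearson 95% CI |
|---|---|---|
| 0/12 | 1 | 0% to 26.5% |
| 1/12 | 0 | 0.2% to 38.5% |
| 6/12 | 0 | 21.1% to 78.9% |
| 12/12 | 0 | 73.5% to 100% |
| 0/36 | 1 | 0% to 9.7% |
| 1/36 | 0 | 0.1% to 14.5% |
| 36/36 | 0 | 90.3% to 100% |

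Reading the Clopper-Pearson citation as a check on whether the interval excludes zero gives the same split: the lower limit is 0 at x = 0 and positive at any x ≥ 1.

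**Error rates.** Under the null the test never rejects, so the type I error is 0, not 5%. The chance of p = 0 is the chance of at least one responder, 1 − (1 − π)^12. This is 11.4% at a true rate of 1%, 46.0% at 5% and 71.8% at 10%.

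**With a non-zero reference (illustration only).** The documents give no reference rate, so 2%, 5% and 10% are assumptions, not suggested benchmarks. The two-sided p that matches the Clopper-Pearson interval is the doubled tail, 2·P(X ≥ x):

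| Reference | Fewest responders of 12 with p < 0.05 | p | Fewest of 13 | p |
|---|---|---|---|---|
| 2% | 2 | 0.046 | 3 | 0.004 |
| 5% | 3 | 0.039 | 3 | 0.049 |
| 10% | 5 | 0.009 | 5 | 0.013 |

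The convention matters. Against 10%, 4/12 gives a doubled-tail p of 0.051, in line with its interval of 9.9% to 65.1%, which includes 10%. The other common exact convention, which sums all outcomes no more likely than the one observed, gives p = 0.026.

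**The case against.** The strongest case on the other side concerns weight and remedy, since the arithmetic is not in dispute.

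- **The informative analysis is already planned.** SAP 3.4.2 provides a proportion with a 95% interval, and the Clopper-Pearson citation in 3.2.1 makes that interval the natural reading. P-values come only where appropriate, so an empty one could be left out. This stands and is why the point is minor. But the qualifier does not exclude categorical outcomes, and the test itself is planned without it.
- **Zero is not an arbitrary null.** Protocol 5.1 requires a Screening IGF-1 of at least 1.3 × ULN, so the proportion at or below 1.2 or 1.0 is essentially zero at entry by design. That explains the choice but does not make the p-value usable. SAP 3.2.1 itself cites variation in IGF-1 between Screening and Day 1, and SAP 3.4.2 defines a subset above 1.3 × ULN at Day 1. The plan thus allows for patients at or below 1.3 × ULN before dosing, and an isolated value at or below 1.2 × ULN could arise without drug effect. The documents do not say how often.
- **Dropping the test departs from the protocol.** Protocol 10.6.3 lists it, and leaving detail to the SAP is not plainly permission to cancel it. SAP 1 promises to document in the study report only departures from the SAP. This stands in part: the change should be declared openly as a departure from Protocol 10.6.3. Keeping a test with a justified non-zero reference would fit the protocol text more closely.

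**Conclusion.** The concern holds. As written, the test yields p = 1 for no responder and p = 0 for any other result, so it cannot do what SAP 3.2.1 asks of it. This follows from the zero null alone and rests on no assumed rate, variance or sample size. The zero null stands in complete, unredacted SAP text, and nothing in Protocol 10.6.3 or SAP 3.4 replaces it.

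Severity is minor. No estimate, interval, sample size or visible decision changes. The harm is confined to a p-value that could be read as strong evidence when one patient in a group responds.

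**What to change.** In SAP 3.2.1, replace the rule for categorical outcomes with wording such as:

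> For categorical efficacy outcomes, counts and proportions will be reported with two-sided 95% Clopper-Pearson confidence intervals. No test against a proportion of zero will be performed.

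Limit the sentence on p-values to the continuous outcomes.

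In SAP 3.4.2, name the interval and keep the present scope:

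> The proportions with IGF-1 ≤ 1.2 × ULN and ≤ 1.0 × ULN, with two-sided 95% Clopper-Pearson intervals, will be given at each scheduled visit in the FAS and PPS, by dose at randomization, by maximum dose received and overall, and in the two subsets (IGF-1 > 1.3 × ULN at Day 1; IGF-1 > 2.5 × ULN at Screening). The exact binomial test named in Protocol 10.6.3 is not performed.

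If a test is wanted, pre-specify a non-zero reference rate with its justification, state the two-sided convention (the doubled tail agrees with the interval), and compute the threshold at the actual n.

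The cost is a few sentences in the SAP and a statement in the study report that the protocol's test was not carried out. Protocol 10.6.3 can be aligned at the next amendment. A separate amendment for this alone would be out of proportion, given the approvals and notifications in Protocol 12.1. All that is lost is a p-value that adds nothing to the responder count.

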1.3. Endpoints

1.3.1. Primary Endpoint

The primary efficacy endpoint is the percent change in IGF-1 from Baseline to Week 27.

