3.2.7. Stratification, Subsets, and Covariates

Eligible Patients will be stratified on Screening serum IGF-1 level (> 2.5 ULN vs. ≤ 2.5 ULN age and sex adjusted by the central lab).

The following covariates may be used for further exploration in subgroups or as covariates:

- Age group (< 65 years vs. ≥ 65 years)
- Race (Caucasian vs non-Caucasian)
- Gender
- Serum IGF-1 level status (>2.5 ULN vs. ≤ 2.5 ULN)

Additional baseline demographic and disease characteristics may also be considered as covariates.

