3.3.3. Sample Size Consideration

Approximately 40 patients are planned to be randomized in the study while considering an estimated 10% overall drop-out rate. Based on the assumption of expected IGF-1 reduction of 27.5% from Baseline with SD of 30% per treatment group, the minimum sample size of 12 evaluable patients per treatment group will provide 80% power to detect the difference between the null hypothesis of no change and the expected reduction using a 2-sided one-sample t-test with a significant level of 5%.

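### If between-dose comparisons are reported, the SAP should commit to continuous baseline IGF-1 as a covariate; it now names only the two-level screening stratum

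*Combined protocol and SAP*

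**What the plan says.** The primary endpoint is relative to baseline: "The primary efficacy endpoint is the percent change in IGF-1 from Baseline to Week 27". SAP 3.1 and 3.3.2 test it within each dose group by a one-sample t-test against zero, with no covariates, and SAP 3.3.3 sizes the trial on that test alone.

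Comparison between dose groups is optional in SAP 3.2.1. If it is done, "Treatment group and the stratification factor are included as the independent variables in the statistical model while comparing among treatment groups". For continuous endpoints the section then allows ANCOVA or ANOVA, depending on the independent variables, or a van Elteren test if the data are far from normal. For dichotomous endpoints it names logistic regression. The stratification factor (SAP 1.1 and 3.2.7) is screening IGF-1, > 2.5 versus <= 2.5 x ULN.

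SAP 3.2.7 lists possible covariates, with IGF-1 again as a two-level status, and adds: "Additional baseline demographic and disease characteristics may also be considered as covariates". SAP 3.2.1 defines baseline IGF-1 as the average of Screening and Day 1. No visible text names that continuous value as a model term.

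**The concern.** Protocol 5.1 admits patients with screening IGF-1 from 1.3 to 5 x ULN. A single cut at 2.5 treats 1.3 and 2.5 as equal, and 2.6 and 5.0 as equal. The stratum also uses Screening only, although the SAP averages two visits because IGF-1 varies between them. The continuous value is scheduled in every patient before dosing.

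Two things are at stake. One is the precision of any reported dose difference in percent change. The other is the responder comparison, in which patients in the same stratum start at very different distances from the threshold. There is also an ordinary pre-specification gap: in an open-label study, a covariate set left open can be chosen after the data are seen.

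**Working it through.** **1. The plan's own figure.** Inputs from SAP 3.3.3: a mean fall of 27.5% and an SD of 30% in each group, from which the SAP concludes that "the minimum sample size of 12 evaluable patients per treatment group will provide 80% power". The standardised effect is 27.5/30 = 0.917. Exact power of the 2-sided 5% one-sample t-test (noncentral t) is 78.2% at n = 11 and 82.4% at n = 12. So 12 is the smallest group size that reaches 80%, and 36/0.9 = 40 randomised. The figure reproduces, and no covariate enters it.

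**2. How much of the baseline information the stratum keeps.** Assume a normally distributed baseline, linearly related to the outcome. If a proportion p lies above the cut z, the share of explained variance kept is f = φ(z)²/[p(1 − p)].
- Even split: f = 0.637.
- 25/75 split: f = 0.539.

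This treats stratum and covariate as the same measurement. Because the stratum uses Screening only, the true share would be somewhat lower.

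**3. Net effect of adding the continuous term (percent change).** Assume three groups of 12 and SD 30 within stratum.
- Residual variance ratio: (1 − r²)/(1 − f r²).
- Cost of estimating one more slope: a factor 1 + 1/30.
- Degrees of freedom go from 32 to 31, so the critical t goes from 2.037 to 2.040.
- CI-width ratio = √[(1 − r²)/(1 − f r²) × 31/30] × 2.040/2.037.

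For example, at r = 0.5 with an even split: 0.75/(1 − 0.637 × 0.25) = 0.892; × 31/30 = 0.922; square root 0.960; × 1.001 = 0.961.

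| r (assumed) | CI-width ratio, even split | CI-width ratio, 25/75 split | Difference detectable with 80% power, even split (points) |
|---|---|---|---|
| stratum only | 1 | 1 | 35.4 |
| 0 | 1.018 | 1.018 | 36.0 |
| 0.3 | 1.000 | 0.995 | 35.4 |
| 0.5 | 0.961 | 0.948 | 34.0 |
| 0.7 | 0.876 | 0.847 | 31.0 |

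The 35.4 points start from a standard error of 30 × √(2/12) = 12.2. Simulation (4,000 runs per setting, stratified allocation, even split) gave 1.018 at r = 0, 1.000 at 0.3 and 0.961 at 0.5. If only two groups run, with 27 evaluable (30 × 0.9, an assumption), the ratio at an even split is 1.025 at r = 0 and break-even moves to about r = 0.35.

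**4. Responder endpoints.** SAP 3.4.1 counts a responder when IGF-1 is at most 1.2 (or 1.0) x ULN. From baseline b, the reduction needed is 100(1 − threshold/b)%. Take the SAP's mean of 27.5 and SD of 30, and assume normality and percent change unrelated to baseline. Then P(response) = Φ[(27.5 − needed)/30].

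| Baseline (x ULN) | Stratum | Needed for 1.2 | P(<= 1.2) | Needed for 1.0 | P(<= 1.0) |
|---|---|---|---|---|---|
| 1.3 | lower | 7.7% | 75% | 23.1% | 56% |
| 2.5 | lower | 52% | 21% | 60% | 14% |
| 2.6 | upper | 53.8% | 19% | 61.5% | 13% |
| 5.0 | upper | 76% | 5% | 80% | 4% |

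The spread within the lower stratum (75% to 21%) is far larger than the step across the cut (21% to 19%). Here baseline matters even with r = 0 for percent change.

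**The case against.** A reader might infer that the SAP excludes continuous baseline IGF-1 and so throws away precision. The documents do not support that.

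- **Exclusion.** Dose group plus a two-level factor would simply be ANOVA, so naming ANCOVA suggests that a continuous covariate was contemplated, and SAP 3.2.7 expressly leaves room for further baseline characteristics. The public text also lacks protocol 10.1 and 10.6.5 and SAP 3.5, so absence from the whole plan cannot be shown. This stands: the gap is a missing commitment.
- **Precision.** The outcome is already divided by baseline, so the usual argument for baseline adjustment of follow-up values does not carry over automatically. No document gives r, and below about 0.3 the added term slightly widens the interval at an even split. This also stands.
- **An unadjusted contrast.** The comparison already adjusts for the IGF-1 stratum, and stratified randomisation limits imbalance in IGF-1. This stands too.
- **Consequence.** The comparison is optional and carries no power claim, and no stated objective names a dose contrast. At r = 0.5 the detectable difference moves only from 35.4 to 34.0 points. This supports calling the point minor.

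The objection does not reach the responder models, where baseline sets the distance to the threshold. Nor does it remove the case for settling the covariates in advance.

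**Conclusion.** The point holds as a minor improvement to an optional analysis: the between-dose models name only dose group and a two-level IGF-1 stratum, while a more informative baseline value is already defined.

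For percent change the benefit is conditional. Over r = 0 to 0.7 it runs from an interval about 2% wider to one about 12% narrower at an even split (about 15% at 25/75). This assumes linearity, a normal baseline, 12 per group and SD 30. A definite loss of precision is not shown. Equal groups of 12 are themselves an assumption, since the rationale for protocol Amendment 3 says that allocation may not be 1:1:1 and that the 80 mg group may not be run.

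For the responder endpoints the case is firmer. Dependence on baseline comes from the definition; the percentages shown also rest on the SAP's mean and SD, normality, and percent change unrelated to baseline. The one-sample primary test, 12 per group and about 40 randomised are unaffected.

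**What to change.** Add to SAP 3.2.1 that, if between-dose results are reported:
- the ANCOVA for percent change will contain dose group, randomisation stratum and continuous baseline IGF-1 (x ULN, on the log scale if skewed);
- the logistic models for the 1.2 and 1.0 x ULN endpoints will also include baseline IGF-1 where it can be estimated, with a stated fallback for sparse data, such as dropping the stratum term first.

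Make SAP 3.2.7 consistent by listing continuous baseline IGF-1 for these models.

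The cost is a few sentences, one degree of freedom and, at worst, an interval for percent change about 2% wider with three groups of 12 (about 2.5% with two groups and 27 evaluable). No new data are needed.
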